## 4. Subjects and Methods

### 4.1. Study Design

This is a prospective, non-randomized study with concurrently enrolled controls involving up to 20 centers in the US to assess the safety and effectiveness of the coflex® Interlaminar Technology for the treatment of at least moderate leg/buttocks/groin pain with or without low back pain in patients with moderate to severe spinal stenosis. Covariate balance will be achieved through a rigorous application of propensity score subclassification.

### 4.2. Number of Subjects

The numbers of patients to be enrolled is 150 patients per group (300 total). This total will be increased by 15% to account for loss-to-follow-up. The sample sizes were increased by an additional 20% in control group and 5% in the study device group to account for trimming of control patients and possible trimming of study device patients during the propensity score design. Therefore, the total enrolled will be 186 coflex patients and 220 decompression control patients for a total enrollment of 406.

Patients will be enrolled into one of the treatment groups (Group A, without additional implant, Group B, with coflex® Interlaminar Technology).

Recruitment of about 5 patients per month is expected. Each site will be required to enroll at least 5 patients.

### 4.3. Inclusion Criteria

1. Radiographic confirmation of at least moderate lumbar stenosis, which narrows the central spinal canal at one or two contiguous levels from L1-L5 that require surgical decompression. Moderate stenosis is defined as > 25% reduction of the antero-posterior dimension compared to the next adjacent normal level, with nerve root crowding compared to the normal level, as determined by the investigator on CT Scan or MRI.\* The patient may have, but is not required to have for inclusion in the study:
  - a. Facet hypertrophy and subarticular recess stenosis at the affected level(s);
  - b. Foraminal stenosis at the affected level(s);
  - c. Up to stable Grade I degenerative spondylolisthesis (Meyerding classification) or equivalent retrolisthesis as determined by flexion/extension X ray:
    - i. For single level disease, there may be up to a stable Grade I spondylolisthesis or equivalent retrolisthesis at the affected level as determined on flexion/extension films by the investigator.
    - ii. For two level disease, there may be up to a stable Grade I spondylolisthesis or equivalent retrolisthesis at only one of the two contiguous affected levels as determined on flexion/extension films by the investigator. Patients with up to stable Grade I spondylolisthesis at two contiguous levels are excluded, but patients with up to Grade I stable spondylolisthesis at one level and equivalent retrolisthesis at the adjacent level may be included.
  - d. Mild lumbar scoliosis (Cobb angle up to 25°)
2. Radiographic confirmation of no angular or translatory instability of the spine (instability as defined by White & Panjabi: Sagittal plane translation >4.5mm or 15% or sagittal plane

rotation >15° at L1-L2, L2-L3, and L3-L4; >20° at L4-L5 based on standing flexion/extension X-rays)

3. VAS back pain score of at least 50 mm on a 100 mm scale.
4. Neurogenic claudication as defined by leg/buttocks or groin pain that can be relieved by flexion such as sitting in a chair.
5. Patient has undergone at least one epidural injection at any prior time point, AND at least 6 months of prior conservative care without adequate and sustained symptom relief.
6. Skeletally mature
7. Oswestry Low Back Pain Disability Questionnaire score of at least 20/50 (40%).
8. Appropriate candidate for treatment using posterior surgical approach.
9. Psychosocially, mentally, and physically able to fully comply with this protocol, including adhering to scheduled visits, treatment plan, completing forms, and other study procedures.
10. Personally signed and dated informed consent document prior to any study-related procedures indicating that the patient has been informed of all pertinent aspects of the trial.

\*The Lumbar Spine (H. Herkowitz ed. 2004, Lippincott Williams, & Wilkins).

#### **4.4. Exclusion Criteria**

1. More than two contiguous vertebral levels requiring surgical decompression.
2. Prior surgical procedure that resulted in translatory instability of the lumbar spine [as defined by White & Panjabi (see Inclusion Criteria, Item #2)].
3. More than one surgical procedure at any combination of lumbar levels.
4. Prior fusion, implantation of a total disc replacement, complete laminectomy, or implantation of an interspinous process device at index lumbar level.
5. Radiographically compromised vertebral bodies at any lumbar level(s) caused by current or past trauma or tumor (e.g., compression fracture).
6. Severe facet hypertrophy that requires extensive bone removal which would cause instability.
7. Isthmic spondylolisthesis or spondylolysis (pars fracture).
8. Degenerative lumbar scoliosis (Cobb angle of greater than 25°).
9. Disc herniation at any lumbar level requiring surgical intervention.
10. Osteopenia: A screening questionnaire for osteopenia, SCORE (Simple Calculated Osteoporosis Risk Estimation), will be used to screen patients who require a DEXA bone mineral density measurement. If DEXA is required\*, exclusion will be defined as a DEXA bone density measured T score of  $\leq -1.0$  (The World Health Organization definition of osteopenia).
11. Back or leg pain of unknown etiology.
12. Axial back pain only, with no leg, buttock, or groin pain.
13. Morbid obesity defined as a body mass index  $> 40$ .
14. Pregnant or interested in becoming pregnant in the next three years.
15. Known allergy to titanium, titanium alloys, or MR contrast agents.
16. Active or chronic infection – systemic or local.

17. Chronically taking medications or any drug known to potentially interfere with bone/soft tissue healing (e.g., steroids), not including a medrol dose pack.
18. History of significant peripheral neuropathy.
19. Significant peripheral vascular disease (e.g., with diminished dorsalis pedis or posterior tibial pulses).
20. Unremitting back pain in *any* position.
21. Uncontrolled diabetes.
22. Known history of Paget's disease, osteomalacia, or any other metabolic bone disease (excluding osteopenia, which is addressed above).
23. Cauda equina syndrome, defined as neural compression causing neurogenic bowel (rectal incontinence) or bladder (bladder retention or incontinence) dysfunction.
24. Fixed and complete motor, sensory, or reflex deficit.
25. Rheumatoid arthritis or other autoimmune diseases.
26. Known or documented history of communicable disease, including AIDS, HIV, active Hepatitis
27. Active malignancy: a patient with a history of any invasive malignancy (except nonmelanoma skin cancer), unless he/she has been treated with curative intent and there has been no clinical signs or symptoms of the malignancy for at least five years. Patients with a primary bony tumor are excluded as well.
28. Prisoner or ward of the state.
29. Subject has a history of substance abuse (e.g., recreational drugs, narcotics, or alcohol).
30. Subject is currently involved in a study of another investigational product for similar purpose.
31. Currently seeking or receiving workman's compensation.
32. In active spinal litigation.

\*Primary location for DEXA scan should be the spine. In the event that the spine T score is in the osteopenic range (-1.0 to -2.5) then a T-Score from the hip may be obtained. If the T-Score from the hip comes back above -1.0 then, at the discretion of the investigator, the patient may be considered for inclusion in the study. Also, a hip DEXA may be used in the event that a spine DEXA cannot be obtained.

#### **4.5. Restriction to Subjects**

There are no study specific restrictions for patients' diet or habits (smoking, etc....).

#### **4.6. Study Conduct**

The study will be performed in up to 20 study centers in the US (10 coflex sites and 10 control sites). All centers are experienced in the treatment of spinal stenosis with decompression surgery and with the coflex® Interlaminar Technology, but no site were included in the IDE study. Each site will enroll either coflex patients or control patients. Sites will be selected for comparability in terms of surgeon and institutional characteristics as well as for expected patient mix characteristics. All treatments will be carried out according to the routine procedures for decompression surgery in each center. Only investigators that are experienced in the implantation of the study device will perform the surgeries for this trial.

Subjects participating in this study will be recruited from the investigators' standard patient populations. Subjects must meet all of the following inclusion criteria and none of the exclusion criteria. The investigator maintains exclusive responsibility for the inclusion and exclusion of any potential study participant.

All patients presenting for treatment of symptomatic spinal stenosis that have not responded to conventional medical therapy will be evaluated for study participation based on the inclusion/exclusion criteria. Subjects will be considered enrolled in the study after informed consent has been signed and at time of surgical incision.

The target enrollment is 406 patients (186 coflex patients and 220 decompression control patients). A minimum of 345 patients are planned to be included in the trial. Each center should recruit at least 5 patients.

The schedule of study related actions is summarized in the Study Timeline (see Section 4.8.9).

Patients who fulfil the in-/exclusion criteria will be enrolled into one of the two concurrent treatment groups.

Group A: decompression surgery without any further stabilization (control group)

Group B: decompression surgery with stabilization using the coflex® Interlaminar Technology (treatment group)

Blood sampling is not planned as a part of the trial but might be performed as part of the routine procedures of each center. Blood parameters will not be documented in the CRF – except if necessary for SAEs.

For the implantation of the coflex® Interlaminar Technology the product brochure and implantation instructions provided by the manufacturer have to be followed.

## 4.7. Description of Study Procedures

### 4.7.1. Surgical Technique

Selective, microsurgical decompression surgery will be performed through a mono- or biportal access based on the experience of the investigators, taking into consideration the individual situation of each patient.

Wing bending pliers provided by Paradigm Spine will be used for controlled bending and crimping of the coflex® implant wings if necessary.

### 4.7.2. X-ray Imaging:

X-ray images will be made **in standing position** in both cohorts.

During visit 1, visit 3, visit 4, visit 5, visit 6, visit 7, and visit 8 X-rays will be taken in the following positions: antero-posterior, lateral, flexion and extension.

During visit 2 (surgery) X-rays will be taken only in group B (with coflex® implant) for the following two positions: antero-posterior and lateral.

In total 30 X-ray images will be made in the course of the trial for group B (with coflex® implant).

In total 28 X-ray images will be made in the course of the trial for group A (without implant; control).

X-ray images from Visit 2, which are only performed in test group B, will not be evaluated on regular basis, but may be consulted on demand for potential assessment of spinous process fractures, implant function and potential migration.

Additional radiographs may be taken in between regularly scheduled visits at the discretion of the investigator/patient's surgeon due to new symptoms. This additional information makes an earlier intervention possible, which could result in an early reduction of the pain and/or in a delay in progression of the illness.

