#### **4.7.7. Central Evaluation of Radiological Images**

Only sites with digital X-ray capability will enroll patients into this study.

---

 Deen H. et al., Measurement of exercise tolerance on the treadmill in patients with symptomatic lumbar spinal stenosis: a useful indicator of functional status and surgical outcome, J. Neurosurg 83:27-30, 1995

 Deen H. et al., Use of the Exercise Treadmill to Measure Baseline Functional Status and Surgical Outcome in Patients With Severe Lumbar Spinal Stenosis, Spine: Volume 23(2) 15 pp 244-248, 1998

In order to achieve a comparable evaluation, all radiological images will be evaluated by a core lab. For evaluation of X-rays a special form “core evaluation of X-rays” is available. All relevant parameters are listed in this special case report form.

X-ray images will be sent electronically to the core lab, either on a CD or via mail or via FTP site.

Anonymized electronic copies will be stored at sponsor and might be used for external reading and evaluation in the future.

Preoperative MRI images, 24 Month CT images, and 60 Month CT images for subjects with symptomatic, confirmed spinous process fracture will also be collected. Fractures are confirmed by the core lab.

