### 4.8.2. Visit 2: Surgery

- Completion of in/exclusion criteria
- Surgery
- Hospitalization information will be collected such as duration of surgery, blood loss and number of days in hospital.

- Discharge Information: Date of discharge, neurological status, pain management, follow-up treatment. X-rays have to be performed before discharge only in group B (with implant) in anterior-posterior and lateral position.
- Exclusion during the decompression surgery:  
In case the surgeon identifies during surgery any circumstance that contradicts to the patient's participation in the trial, the surgeon has to exclude the patient from the trial participation. Possible exclusion reasons are:
  - Instabilities assessed during surgery that requires stabilization by spinal fusion.
  - Partial resection or resection of disc tissue (see exclusion criterion 2).
  - (S)AEs assessed during surgery that rule out the implantation of coflex® (e.g. breakage of a spinal process, local osteoporosis).
- As these patients had been enrolled an eCRF will be filled in. The study monitor will only check the signed informed consent form and patient demographics as well as the reason of failure. The patient will be a dropout and the dropout reason will be recorded in the eCRF.

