#### **5.2.6. Migration**

Assessment of significant migration of the implant or complete expulsion (significant is defined  $> 5$  mm) will be assessed from X-ray images (point of reference is the tip of the U-portion implant identified on the corresponding X-ray image). Baseline images will be made before discharge of the patient. Further images will be made after 3 months and after 24 months, and annually thereafter. All X-ray images from all centers will be evaluated centrally by an experienced radiologist.

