#### **5.2.7. Spinous Process Fracture**

Spinous process fractures will be assessed from X-ray at all time points and CT at 24 months. Subjects with confirmed, symptomatic spinous process fractures will also have CT taken at 60 months. All X-rays and CTs from all centers will be evaluated centrally by an experienced, independent radiologist. Presence of spinous process fractures will not be considered a treatment failure.

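### Section 4.7.2 exempts the pre-discharge film, the baseline for implant migration, from routine reading, which contradicts Sections 5.2.6, 4.7.7 and 5.2.7

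*Combined protocol and SAP*

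**What the plan says.** All references are to the combined protocol and SAP.

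- **Which film is the baseline.** Section 5.2.6, on migration: "Baseline images will be made before discharge of the patient". Displacement is judged from the tip of the implant's U-shaped portion and counts as significant above 5 mm. Complete expulsion also counts.
- **When that film is taken.** Section 4.8.2 places it at Visit 2: "X-rays have to be performed before discharge only in group B (with implant) in anterior-posterior and lateral position".
- **Whether it is read.** Section 4.7.2: "X-ray images from Visit 2, which are only performed in test group B, will not be evaluated on regular basis". The same sentence goes on to say that the films "may be consulted on demand for potential assessment of spinous process fractures, implant function and potential migration".
- **What is said elsewhere about reading.** Section 4.7.7: "all radiological images will be evaluated by a core lab". Section 5.2.6 likewise has the X-rays of all centers evaluated centrally. Section 5.2.7: "Spinous process fractures will be assessed from X-ray at all time points".
- **Later migration images.** Section 5.2.6: "Further images will be made after 3 months and after 24 months, and annually thereafter". Month 12 is not in that list, although Sections 4.7.2, 4.8.4 and 4.8.10 schedule a four-view X-ray at that visit.

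**The concern.** Migration is a change in position, so it needs a reference position. The Visit 1 films are taken before surgery and show no implant. The Visit 2 film is the only scheduled film of the implant as it was placed, and the next one is at Month 3. A rule that leaves the Visit 2 film unread unless someone asks for it removes the routine reference reading from an endpoint that Section 5.2.6 defines by that film.

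Migration or expulsion and spinous process fracture are listed radiographic endpoints (Section 3.3). Displacement of the implant is a device risk named in Sections 1 and 6.1, and the study is an FDA-mandated post-approval evaluation. If the baseline is read in some patients and not in others, with no stated rule for which, the migration rate becomes hard to interpret.

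**Working it through.** **Step 1: reproduce the film counts in Section 4.7.2.** Seven visits (1, 3, 4, 5, 6, 7, 8) have four views each, and Visit 2 adds two views in group B only.

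- Group A: 7 x 4 = 28. The plan states 28.
- Group B: 28 + 2 = 30. The plan states 30.

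Both match, so the Visit 2 films are part of the planned imaging.

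**Step 2: set the reading rules side by side, per coflex patient.**

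| Section | Films routinely read |
|---|---|
| 4.7.2 | 30 - 2 = 28 |
| 4.7.7 and 5.2.6 | 30 |

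The two films in dispute are the baseline for migration. Section 5.2.7 sides with the second row for fracture, since Visit 2 is one of the time points at which an X-ray is taken.

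**Step 3: number of films.** Planned coflex enrollment is 186 (Sections 4.2 and 4.6). Films in dispute: 186 x 2 = 372 at full enrollment.

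**Step 4: the interval affected.** The Visit 3 window is 3 months ± 2 weeks, so the first routinely read film that shows the implant can come as late as 3 months + 2 weeks, about 3.5 months after surgery.

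**Step 5: effect on the criterion.** Let d1 be the displacement from the Visit 2 film to the Month 3 film, and d2 the displacement from Month 3 to a later film, in the same direction. Section 5.2.6 asks whether d1 + d2 > 5 mm. If the Visit 2 film is not read and Month 3 serves in its place, the question becomes whether d2 > 5 mm. Two hypothetical cases:

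- d1 = 6, d2 = 0: the total of 6 mm meets the criterion, but 0 mm is measured, so the case is not counted.
- d1 = 3, d2 = 3: the total of 6 mm meets the criterion, but 3 mm is measured, so the case is not counted.

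The documents give neither the share of displacement that occurs before Month 3 nor an expected migration rate. These cases therefore show the direction of the effect and not its size.

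**The case against.** The strongest reply is that Section 5.2.6 is the endpoint's own section. It names the pre-discharge baseline and requires central reading of all X-rays, and Section 4.7.7 agrees. On that reading Section 4.7.2 is a stray sentence and nothing is lost. Even under Section 4.7.2 the films may be consulted for migration. Electronic copies are stored with the sponsor (Section 4.7.7) and X-ray data are kept for at least 30 years (Section 4.15.2). Expulsion or gross displacement might be visible at Month 3 without a baseline. Movement that leads to revision or removal at the index level is captured separately (Section 5.1.2). The Radiographic Protocol (Appendix V) and the core-lab form are not among the documents reviewed and may name the reference film.

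Much of this stands, and it rules out several stronger inferences a reader might draw:

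- **That early displacement cannot be detected.** It can, because the films exist and may be read on demand or later. What is missing under Section 4.7.2 is systematic reading.
- **That Month 3 is the plan's reference film.** No section says so. It would be the working reference only by default.
- **That on-demand reading depends on symptoms.** Section 4.7.2 states no trigger and does not say who may ask. Its mention of new symptoms concerns additional unscheduled radiographs. Selective ascertainment is a risk and not a stated rule.
- **That a perioperative fracture would have no dated first observation.** Adverse events are recorded from incision with start dates (Section 6.1), breakage of a spinal process during surgery is among the listed reasons for exclusion (Section 4.8.2), Month 3 films are taken, and all subjects have CT at Month 24. At most, an unrecognized early fracture is first seen at Month 3.

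The reply does not remove the contradiction. The sentence in Section 4.7.2 is specific to Visit 2 and can reasonably be read as an exception to the general statements about all images. A core lab could follow either.

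**Conclusion.** The sections contradict each other on whether the migration baseline is routinely read. The consequence is conditional: if Section 4.7.2 governs and the stored films are not otherwise consulted, displacement over up to about 3.5 months after surgery is not systematically measured in up to 186 coflex patients. The reported migration rate could then be too low, or could depend on whose films happened to be requested. The size of any understatement cannot be given from the documents.

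The reach is limited. Migration is a secondary endpoint, Section 7.9 plans descriptive summaries for secondary endpoints, and migration is not a component of composite clinical success at Month 24 or Month 60 (Sections 3.2 and 5.1). No hypothesis test, power or type 1 error figure changes. The conclusion rests on the main text alone; Appendix V might settle the reading rule in practice, but the conflict in the main text would remain.

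**What to change.** 1. In Section 4.7.2, replace the sentence on non-routine evaluation with a statement that the core lab reads the Visit 2 antero-posterior and lateral films of every coflex patient, as the reference for the 5 mm criterion and for early fracture status. This brings it into line with Sections 4.7.7, 5.2.6 and 5.2.7.
2. In Section 5.2.6, add the already scheduled Month 12 film to the list of migration images.
3. Check that Appendix V and the core-lab form name the same reference film.

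The cost is a wording change and core-lab reading of at most 372 films, which are already due to be taken and which Sections 4.7.7 and 5.2.6 already promise to read. No visit, image or radiation exposure is added. The reported migration rate may come out higher.

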#### 4.7.3. Questionnaires

- The **Oswestry Low Back Pain Disability Index (ODI)** will be used. The ODI is a self-rating patient questionnaire developed to assess the impairment on patients' life by low back pain. The ODI is used as part of the primary effectiveness endpoint of this trial.
- The **Zurich Claudication Questionnaire (ZCQ)** will be used as a self-rating patient questionnaire to assess the impact of pain on patient's everyday life. The ZCQ includes questions that are used to produce indices of symptom severity, physical functional status and patient satisfaction.
- **Visual Analog Scales (VAS)** will be used. They comprise of a 100 mm horizontal line which is scaled from 0 (left end) to 10 (right end). Every VAS is associated with a single question. The patient will be asked to mark his subjective impression about the question asked by a small vertical line on the VAS. For evaluation the distance of this marking from the left end of the VAS will be measured in mm with a ruler. VAS questions include right leg pain, left leg pain, and back pain.
- The **EQ-5D** will be used. The EQ-5D consists of 5 questions and a drawn scale to measure the patient's quality of life.

